### **3.7. Blinding assessment**

At the end of the follow-up period, female head of household or primary care giver will be asked to identify which tablet they had received. Success of blinding will be measured using two different approaches: James' blinding index is a variant of the kappa statistics and has been previously used in blinded trials of household water treatment (James et al 1996; Colford 2002). Bang's blinding index consists of estimating, for each treatment group, the proportion of correct guesses beyond chance (Bang et al. 2004).

### **3.8. Sample size calculations**

Our primary outcome is the mean longitudinal prevalence of diarrhea, expressed as the number of weeks with diarrhea divided by the number of weeks under observation. The number of children < 5 required in each group was derived using the standard formulae for comparison of two means:

$$n = (z_{\alpha/2} + z_{\beta})^2 (sd_0^2 + sd_1^2) / (m_0 - m_1)^2$$

where  $m_0$  and  $m_1$  are the means longitudinal prevalence of diarrhoea among the control and intervention group, respectively and  $sd$  their standard deviation.

Based on the results from recent studies on household water treatment (Hunter 2009, Mausezahl 2009), we powered the study to detect a 15% reduction in the mean longitudinal prevalence of diarrhea among the intervention arm. Our calculation assumes 80% power, significance level  $\alpha=0.05$ , mean longitudinal prevalence of diarrhoea of 4% among children < 5 years at baseline, a coefficient of variation ( $sd/mean$ ) = 1.1, design effect of 1.1 for clustering of diarrhoea cases at the household level, 15% lost to follow-up. The sample size will be increased to account for 3-day recall period and intermittent sampling (Schmidt 2010). Based on the above assumptions, we estimated that we need at least 1500 children < 5 per arm (3000 in total). Assuming 1.5 <5s per household, the number of households to be recruited is approximately 1000 per arm. The sample size will be adjusted according to the baseline diarrhoea estimates obtained during the six-week pilot study.

### **3.9. Data Analysis**

Data will double-entered in Epidata, will be checked for consistency and accuracy and will be analyzed in Stata 11.0 (Stata Corporation, College Station, Texas, US). The primary analysis is intention-to-treat; comparing the mean longitudinal prevalence of diarrhoea among children <5 in the intervention versus control groups. Diarrhoea among participants of all ages will also be reported. We will use generalized estimating equations (GEE) to calculate longitudinal prevalence ratio accounting for clustering at the household level. The effect of the intervention on WAZ will be assessed using random effect linear regression adjusting for baseline WAZ measurement. Any association between WAZ and number of days with diarrhoea in the previous 3 days will be explored using GEE with number of days included as a categorical variable. Statistical analyses of microbiological data are conducted after  $\log_{10}$  transformation of TTC count values to account for the skewed distribution. Comparison between groups will be conducted using non-parametric tests if the distribution is not normal after log transformation. Subgroup analysis will be conducted to 1) measure the effect of compliance on diarrhea and 2) explore the relationship between faecal contamination levels and risk of diarrhoea.

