### **3.5. The Intervention**

Aquatabs are tablets formed from sodium dichloroisocyanurate (NaDCC) and an effervescent base. Widely used for decades in household and commercial laundry bleaches, scouring powders and industrial and recreational water disinfection, NaDCC has recently found applications ranging from sanitizing medical instruments to cleaning of baby bottles and contact lenses. For more than 30 years, Aquatabs have been used for the emergency treatment of water. Its widespread use in non-emergency household water treatment applications began after acceptance of the chlorinated isocyanurates by the United States Environmental Protection Agency (USEPA), WHO and the Food and Agriculture Organization of the United Nations for the routine treatment of drinking water. NaDCC may also offer certain other advantages over sodium hypochlorite in terms of safety, shelf life, up-front cost and convenience, although these have not yet been shown to impact coverage or uptake ([name] & Edmondson 2006).

Chlorine tablets such as Aquatabs may present a unique opportunity for blinding a household water treatment intervention in low-income settings. Tablets can be manufactured with the effervescent base and no NaDCC and packaged in a manner identical to Aquatabs. Other blinded trials conducted in low-income settings used liquid sodium hypochlorite that may have been noticeable to study participants due to the strong odour of the agent (Kirchoff 1985; Austin 1993). However, prior field trials of Aquatabs showed no evidence that intervention and control populations could detect whether they were using the tablets containing NaDCC (Jain 2010).

Each participating household will be provided with sufficient supplies of Aquatabs or placebos free of charge. Supplies of tablets at the household will be counted by the distributors every two weeks during their visit and topped off to cover the following two weeks. Households will also receive instructions on the use of the same in accordance with the manufacturers instructions and PSI's experience. Consistent with its normal practices, representatives of PSI will make regular visits to participating communities to ensure that they have adequate supplies. The study participants will be advised prior to the commencement of the study that half of the study households will receive a placebo. For this reason, they will be encouraged to continue

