#### **3.6.4. Compliance**

Compliance will be assessed in two ways: 1) by asking the respondent (primary care giver of the child) if the child's drinking water has been treated and if so, the method that was used 2) by measuring presence of residual free chlorine in household water storage container. Chlorine testing will be conducted in a similar way in control and intervention households. Measuring chlorine in the control arm will help assessing neutrality of the placebo tablets and monitor any potential contamination due to exchange of the tablets between households. Concentration of free chlorine in the water will be measured to monitor dosage levels among intervention households. Chlorine will be assessed using a colorimetric indicator and DPD1 reagent (Palintest Limited).

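### The planned compliance subgroup analysis targets an effect but groups households on post-randomisation behaviour, so it is liable to confounding; an allocation-based estimate should replace it

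*Protocol*

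**What the plan says.** Section 3.9 makes intention-to-treat primary: "The primary analysis is intention-to-treat; comparing the mean longitudinal prevalence of diarrhoea among children <5 in the intervention versus control groups". It then adds a secondary item: "Subgroup analysis will be conducted to 1) measure the effect of compliance on diarrhea". It does not say which groups are compared or how compliance is defined, and it carries no exploratory label. The second item in the same sentence, on faecal contamination, only sets out to explore a relationship.

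Section 3.6.4 gives two compliance measures. One is caregiver report, obtained "by asking the respondent (primary care giver of the child) if the child's drinking water has been treated" and by what method. The other is objective: "by measuring presence of residual free chlorine in household water storage container". Both arms are tested: "Chlorine testing will be conducted in a similar way in control and intervention households". The reasons given for testing controls are to check that the placebo is neutral and to "monitor any potential contamination due to exchange of the tablets between households".

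On the placebo, Section 3.5 says: "Tablets can be manufactured with the effervescent base and no NaDCC". The same section describes a third source of information on use, which Section 3.6.4 does not list as a compliance measure: "Supplies of tablets at the household will be counted by the distributors every two weeks during their visit".

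**The concern.** The protocol fixes a method (subgrouping) and a causal target (an effect of compliance). Households that treat water reliably may also differ in hygiene, income or child care, and each of these can change diarrhoea without any help from the tablet. A subgroup formed on such behaviour can show an apparent benefit from an inert tablet, or hide a real one.

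The objective measure makes this harder to avoid. A positive chlorine test shows use of active tablets; it cannot show use of placebo tablets. If chlorine defines compliance, the comparable placebo households cannot be found, and the contrasts left are the two that are open to confounding.

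Section 1.2 reports that earlier blinded trials found no protective effect on diarrhoea, including one of these tablets in Ghana. If the primary result here is also null, a compliance effect could be given more weight than it can bear.

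**Working it through.** The protocol states no figure for this analysis, so there is none to reproduce. The check has three parts.

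**1. What each measure can identify**

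| Measure | Active arm | Placebo arm |
|---|---|---|
| Residual free chlorine (3.6.4) | Shows tablet use | Cannot show placebo use; a positive points to tablet exchange or the household's own treatment |
| Caregiver report (3.6.4) | Can be positive | Can be positive |
| Two-weekly tablet count (3.5) | Shows tablets gone from stock | Same, but not listed as a compliance measure |

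In the earlier Bangladesh trial cited in Section 1.2, all 188 intervention samples and no control samples were chlorine-positive. Few control positives are therefore to be expected here, though that is another trial's result.

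**2. Size of a false effect when the tablet does nothing**

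Let p be the proportion complying and r the ratio of compliers' underlying diarrhoea to that of non-compliers. With no tablet effect:

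- compliers vs non-compliers in the active arm: ratio = r
- active compliers vs all controls: ratio = r / (p·r + 1 − p)

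As one assumed point, p = 0.7 and r = 0.8 give 0.80 for the first. The second is 0.80 / (0.7 × 0.8 + 0.3) = 0.80 / 0.86 = 0.93.

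For a range, 200,000 children were simulated with a true effect of zero and about 60% compliance. One household trait raised compliance (log-odds per SD) and lowered diarrhoea (log rate per SD). These values are assumptions; none comes from the protocol.

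| Trait on diarrhoea | Trait on compliance | Active compliers vs non-compliers | Active compliers vs all controls | Compliers vs compliers, same measure in both arms | Intention-to-treat |
|---|---|---|---|---|---|
| 0.2 | 0.5 | 0.911 | 0.963 | 1.001 | 1.002 |
| 0.2 | 1.0 | 0.849 | 0.932 | 1.002 | 1.002 |
| 0.4 | 0.5 | 0.830 | 0.926 | 1.005 | 1.003 |
| 0.4 | 1.0 | 0.719 | 0.863 | 1.003 | 1.003 |

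When the trait affected only compliance, only diarrhoea, or neither, every ratio was about 1.00. The formula agrees with the simulation: p = 0.6 and r = 0.719 give 0.719 / (0.4314 + 0.4) = 0.865, against 0.863 simulated.

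For comparison, Section 3.8 powers the trial for a 15% reduction from 4%, that is 3.4 / 4.0 = 0.85. Compliers versus non-compliers reached or passed this in three of the four settings (0.849, 0.830, 0.719). Active compliers versus all controls came close only in the most confounded setting (0.863).

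The compliers-versus-compliers column is near 1.00 because the simulation let compliance depend on the household and not on allocation. It does not show that this contrast is safe if allocation changes compliance.

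**3. What an allocation-based estimate does**

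Complier-average effect = (active mean − control mean) / (proportion chlorine-positive in active − proportion in control).

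- If the tablet does nothing, the numerator is expected to be zero, and so is the estimate, however compliers differ from others.
- If the target difference holds (3.4% − 4.0% = −0.6 percentage points) and the chlorine difference is an assumed 0.60, the estimate is −0.6 / 0.60 = −1.0 percentage point. With the denominator taken as known, the interval is 1 / 0.60 = 1.67 times as wide as the intention-to-treat interval for the difference.

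**The case against.** The strongest reply is that Section 3.9 devotes one clause to this and names no contrast. Complier versus non-complier, and active complier versus all controls, are readings of the clause, and an analysis plan that is not shown may specify something better. The analysis is not primary, and the effect of compliance on diarrhoea is not among the objectives in Section 2, which asks only how far the tablets are used correctly and consistently. Caregiver report, which works in both arms, is already planned.

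Much of this stands. The missing definitions alone would not be a finding. What remains is that the protocol itself chooses subgrouping and sets out to measure an effect. Any subgroup formed on household behaviour after randomisation loses its protection, whichever measure is used.

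A reader might infer four stronger points that the protocol does not support:

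- **That chlorine cannot be positive in the placebo arm.** Section 3.6.4 tests that arm partly to detect tablet exchange, and Section 3.5 encourages households to keep up their existing water treatment. Chlorine cannot reflect placebo-tablet use; that is all.
- **That the analysis must be confounded.** Bias needs a shared cause of compliance and diarrhoea, and a contrast that exposes it.
- **That the main result is at risk.** Intention-to-treat does not use compliance.
- **That comparing arms within a compliance level restores randomisation.** It does so only if allocation leaves compliance unchanged. The pilot (Section 3.1) looks at acceptability of taste and at blinding, so the protocol itself treats this as an open question.

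**Conclusion.** The concern holds in a limited form. The planned analysis is liable to confounding because it groups households on post-randomisation behaviour while aiming at an effect, and a complier group defined by chlorine has no placebo counterpart. With no true effect, the assumed settings gave false ratios of 0.91 to 0.72 for compliers versus non-compliers and 0.96 to 0.86 for active compliers versus all controls, against a target of 0.85. These show what is possible and do not predict this trial: they depend on about 60% compliance, on the assumed strength of the shared trait, and on which contrast is used. The intention-to-treat conclusion is untouched. This is a cheap and worthwhile improvement to a secondary analysis, not a threat to the trial.

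**What to change.** Amend Section 3.9 as follows.

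1. Replace the compliance subgroup analysis with a complier-average effect on diarrhoea, using allocation as instrument and residual chlorine positivity, summarised by arm, as treatment received. Allow for household clustering. State the exclusion restriction: allocation affects diarrhoea only through chlorination of the water. Subtracting control-arm positivity takes account of tablet exchange and existing treatment.
2. Label any contrast by observed compliance, including chlorine-positive versus chlorine-negative, as exploratory and non-randomised.
3. If the arms are also compared within compliance levels, define compliance identically in both, from caregiver report or from the two-weekly tablet counts if these are entered as data. State the assumption that allocation does not affect compliance. Check it by comparing compliance between arms and by the blinding indices in Section 3.7.

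The cost is a wording change, a little programming and wider intervals. If tablet counts are used, they must be entered as data, and Section 4.1, which gives the implementing organisation no role in data collection, needs an exception where its distributors supply the counts.

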### **3.10. Quality controls**

Field staff will be extensively trained at the start of the trial. The training will cover basic epidemiological concepts and methods, ethics, interviewing techniques, weight measurement, water testing, data recording. Field supervisors will conduct unannounced random visits and re-interview 5% of respondents during the study period. 10% of weight measurements and 5% of water tests will also be done in duplicates. Regular meetings with the field team will be held to review progresses, discuss and resolve any issues encountered.

### **3.11. Ethics**

Ethical approval will be sought from the ethics committee at the London school of Hygiene and Tropical Medicine and from the ethics committee at the Indian Institute for Health Management Research. The trials will be registered on <http://clinicaltrials.gov/>

## **4. STUDY PARTICIPANTS AND STAFFING**

### **4.1. Study Participants**

This study will be conducted by representatives of the London School of Hygiene & Tropical Medicine (LSHTM), a leader in research concerning water, sanitation and hygiene interventions in low-income settings. They will be working in collaboration with the Indian Institute of Health Management Research, a leading public health institute in India.

The intervention will be implemented by Population Services International (PSI), a US-based non-governmental organization with offices in New Delhi and extensive operations in India. PSI has broad experience with household water treatment interventions in 21 countries in Asia and Africa. It also has extensive experience with using and promoting Aquatabs. PSI's communication and behaviour change campaign will be designed with assistance from US-based Partners for Appropriate Technologies in Health (PATH). PATH is engaged in India and elsewhere on a Gates-funded learning initiative on household water treatment

Additional financial support for the trial will be provided by PATH, the United States Agency for International Development, Medentech, Ltd. and the American Chemistry Council. Neither PSI nor any of the other financial supports for the trial will play any role in the collection or analysis of the data or in the preparation of the reports or papers presenting the results of the study.

